2. STUDY DESIGN

This study will use a double blind, stratified randomization trial approach involving 36 T2D-HF patients taking standard HF therapies, who will be allocated to either ertugliflozin or placebo in a 1:1 ratio (Table 1 – inclusion and exclusion criteria). For feasibility, participants will be recruited from the >4000 HF patients followed at UHN-MSH heart failure clinics and from heart failure clinics in Groningen, the Netherlands, of whom >40% have T2D. The study will consist of a screening visit, a 4-week run-in phase for those subjects not on stable ACEi/ARB treatment, followed by a 12-week double blind treatment period.

The target population will be invited for screening. Subjects who meet all entry criteria and who are already on a stable dose (no changes in dose or type of drug) of ACEis or ARBs for at least 4 weeks proceed directly to randomization. Subjects who had their ACEi or ARB medication changed during the preceding 4 weeks of the screening visit proceed to a run-in phase during which the type and dose of these drugs are stabilized. Subjects will be randomly assigned to one of the two treatments. Subjects will have their study visit in the morning in fasted condition.

Subjects will be instructed to take the study medication once daily, in the morning, except on study days; on those days, the study drug will be taken after the patient visit.

Measurements:

- During the double blind treatment period, patients will collect a 24-hour urine collection at each visit for measurement of 24-hour protein, albumin, glucose, sodium, potassium, creatinine, and urea excretion. Twenty-four hour urine collections will be performed at: Visits 3, 4 and 8. Routine biochemistry and safety labs will be drawn at screening, during each physiological assessment and at each the specified office safety visits (see visit schedule table below).
- Office systolic and diastolic blood pressure measurements, heart rate, weight, and waist circumference will be performed at screening and at each subsequent physiological testing day and at each office visit (see visit schedule table below).
- Blood will be drawn for measurement of renal function tests, HbA1c, glucose, complete blood count, plasma albumin, RAAS biomarkers, natriuretic peptides, and neurohormones on visits 3, 4 and 8.
- Blood and urine samples will be stored for future exploratory biomarker analyses to study the effect of ertugliflozin in this study population.

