The randomization visit procedures should be completed on a single day under a euglycemic clamp. As part of the study procedures, blood glucose will therefore be maintained between 4-6 mmol/L during the long study days. From a patient perspective, the procedures involved in the trial involve three intravenous needles (for renal function assessments, infusion of insulin and dextrose and finally for blood-letting). The randomization visit procedures will include measures of natriuresis, renal and systemic hemodynamic function, neurohormonal assessments, echocardiography, arterial stiffness, plasma volume, bioimpedence spectroscopy, vital signs, weight and waist circumference, blood and urine samples collection. Cardiac output and systemic vascular resistance will also be measured using non-invasive cardiac monitoring (NICOM). This Version number: 6.0

non-invasive technique is a form of bioelectrical impedance ("bioreatance") to measure thoracic fluid content with electrocardiogram electrode stickers. Beat-to-beat changes in fluid content can be used to derive cardiac output. Then, using measured mean arterial pressure, systemic vascular resistance can be calculated. This entire measurement process takes approximately 15 minutes^{8a}. The first dose of blinded study medication should only be administered one day after all randomization visit procedures have been completed.

Visit 4, 5 and 6

One week after initiation of ertugliflozin/placebo, subjects will return to the renal physiology laboratory for the 1-week assessment (Visit 4), with repeated measures of all physiological parameters described for Visit 3. They will then continue the same treatment allocation for the rest of the trial. A safety visit (vital signs, weight, waist circumference, and physical exam and safety laboratory tests) will be conducted approximately 7-10 days later (Visit 5), and again 4-5 weeks later (Visit 6).

Additional telephone visits will be scheduled as required to follow weight and home blood pressure, in line with usual clinical care. If the patient does not tolerate medication a visit to the out-patient clinic will be scheduled. At the end of the treatment period (at visits 3, 4, and 8), the patient will take study medication *BEFORE* physiological procedures are performed.

Visit 7 and 8

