- 0. Summary of baseline demographic and clinical characteristics separated by ertugliflozin group and placebo group will be generated. Significance testing between-group will be performed. The following variables will be included:
 - *Age, sex, weight, waist circumference, BMI, HbA1c, hemoglobin, fasting blood glucose*
 - race (white/black/Hispanic/Asian/other)
 - SBP, DBP, HR
 - Mean eGFR
 - UACR (median and IQR)
 - Concomitant medication (ACEi, ARB, Diuretic, statin)

1. Analysis for the primary objective:

- 1.1. To assess ertugliflozin-related acute and chronic changes in the primary outcome FE(Li+) compared to placebo, linear mixed-effects models will be used. Two separate models will be fit. For acute change, the vector of outcomes will include the baseline and 1-week values (i.e. Visit 3 and Visit 4 values). For chronic changes, the vector of outcomes will include the baseline and 12-week values (i.e. Visit 3 and Visit 8 values). The covariates will include the visit and treatment-by-visit interaction; due to randomization, a covariate for the main effect of treatment will not be included. The treatment-by-time coefficient, its 95% confidence interval, and its p-value will be used to assess the effect of treatment.
- 1.2. We will repeat this analysis with:
 - a. FE(Na+) as an outcome
 - b. FE(Na+) FE(Li+) as an outcome
- 1.3. In exploratory analysis to determine the overall effect of ertugliflozin across all timepoints, we will repeat the above analysis with one model where the vector of outcomes will include all data collected at baseline, 1-week, and 12-week values.

2. Analysis for secondary objective:

- 2.1. Linear regression will be performed with change in volume as the dependent variable and change in FE(Li+) as the independent variable, with treatment as a covariate. Two separate models will be fit for acute and chronic changes. Acute changes will use the baseline and 1-week values for both the dependent and independent variable values; chronic changes will use baseline and 12-week values.
- 2.2. The same models described in the analysis of secondary objective 2.1 will be completed, with changes in PV or ECF as independent predictors, for neurohormones as the dependent variables/outcomes.
- 2.3. 2.6. The same models described in the analysis of primary objective 1.1 and 1.3 will be completed for each of the different outcomes.

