- 2.7.The numbers of hypoglycemic events and serious adverse events will be reported for both the placebo group and ertugliflozin group. No statistical comparisons will be performed.

3. Analysis for exploratory objective:

- 3.1.– 3.3. The same models described in the analysis of primary objective 1.1 and 1.3 will be performed for each of the different outcomes.
- 3.4. The same models described in the analysis of secondary objective 2.1 will be completed, with changes in neurohormones as independent predictors, for changes in absolute measure of renal function as the dependent variables/outcomes.
- 3.5. The same models described in the analysis of secondary objective 2.1 will be completed, with changes in neuro-hemodynamic markers as independent predictors and changes in arterial stiffness as the different dependent variables/outcomes.

- 3.6. The same models described in the analysis of secondary objective 2.1 will be completed, with changes in neurohormones as independent predictors and changes to blood pressure as dependent variable/outcome.
- 3.7.– 3.8. The same models described in the analysis of primary objective 1.1 and 1.3 will be completed for each of the different outcomes.

Analysis population: The intention to treat population will be used for all analyses. There are no planned subgroup analyses for the primary outcome.

Hypothesis testing: For hypothesis testing, a 5% significance level will be used (two-sided). No interim analyses will be performed. For secondary objectives, nominal p-values will be reported.

General model assumptions and model diagnostic procedures: For the linear mixed-effects models with visit and treatment-by-visit interaction as covariates, a participant-level random intercept will be included. Restricted-maximum-likelihood will be used for estimation and the missing-at-random framework will be assumed. Plots of marginal and conditional residuals will be used for model diagnostics and assessment. Similar diagnostic procedures will be used for the linear regression models.

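### The SAP efficacy models use only Visits 3, 4 and 8, so the exploratory overall effect ignores on-drug values scheduled at Visits 5 and 6, and a few listed outcomes may have no usable post-baseline data

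*SAP*

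**What the plan says.** **Models.** SAP analysis 1.1 fits two models. In the acute one, "the vector of outcomes will include the baseline and 1-week values (i.e. Visit 3 and Visit 4 values"); the chronic one pairs Visit 3 with Visit 8. Analysis 1.3 combines the three visits and is introduced thus: "In exploratory analysis to determine the overall effect of ertugliflozin across all timepoints". Its data are limited in the same way: "the vector of outcomes will include all data collected at baseline, 1-week, and 12-week values". Baseline is constrained equal between arms ("due to randomization, a covariate for the main effect of treatment will not be included"), and for correlation "a participant-level random intercept will be included".

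**Reuse.** For secondary outcomes 2.3-2.6 the SAP states: "The same models described in the analysis of primary objective 1.1 and 1.3 will be completed for each of the different outcomes". Parallel sentences cover 3.1-3.3 and 3.7-3.8. The outcomes reached this way include hematocrit (2.3), SBP and DBP (2.4), heart rate (2.5), Strauss plasma volume (3.1), BNP, hemoglobin, creatinine and bicarbonate (3.3), and weight, waist, HbA1c, AST, ALT and electrolytes (3.8).

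**Data collected.** Protocol section 2, on Visits 4, 5 and 6, says: "A safety visit (vital signs, weight, waist circumference, and physical exam and safety laboratory tests) will be conducted approximately 7-10 days later (Visit 5"), with Visit 6 four to five weeks later. The Measurements list says that blood pressure, heart rate, weight and waist "will be performed at screening and at each subsequent physiological testing day and at each office visit". Appendix A lists blood count, BNP, creatinine, sodium, potassium, urea, phosphate and calcium at Visits 3, 4, 5, 6 and 8.

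**The concern.** Visits 5 and 6 fall on treatment, between day 7 and day 84. A model described as covering all timepoints omits both. In a 36-patient trial, repeated measurements are a cheap source of precision, and the protocol's own objectives note that the effects of this drug class may change over time. A patient lost after day 42 contributes only the baseline value to the chronic model, although later on-drug values exist.

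The second problem is more basic. If Appendix A is the operative laboratory schedule, some outcomes named in the SAP are not drawn at Visit 4 or Visit 8. The planned models would then have no post-baseline value for them.

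**Working it through.** The plan states no precision figure for the overall effect, so there is none to reproduce. The documents give no within-patient correlation ρ; every value below is an assumption.

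**1. Which outcomes have which visits (Appendix A and the protocol section 2 schedule).**

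| Outcome | Baseline and on-drug visits listed | Seen by 1.1 and 1.3 |
|---|---|---|
| SBP, DBP, heart rate, weight, waist | 3, 4, 5, 6, 8 | 3, 4, 8 |
| Blood count, BNP, creatinine, sodium, potassium, urea, phosphate, calcium | 3, 4, 5, 6, 8 | 3, 4, 8 |
| AST, ALT, bicarbonate, chloride | 3, 5, 6 | 3 only |
| HbA1c | Appendix A: 3, 5, 6; section 2 Measurements: 3, 4, 8 | passages conflict |
| FE(Li) | 3, 4, 8 | 3, 4, 8 |

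Visit 9 comes one week after study drug stops, so it is not an on-drug value.

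**2. Precision under the SAP's own model.** A random intercept implies equal variance and one correlation ρ between all visits. With baseline constrained equal, the variance of the average effect over m on-drug visits is

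(2σ²/n) × [(1 + (m − 1)ρ)/m − ρ²].

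The ratio of m = 4 (Visits 4, 5, 6, 8) to m = 2 (Visits 4, 8) simplifies to (1 + 4ρ) / (2(1 + 2ρ)).

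| ρ | Bracket, m = 2 | Bracket, m = 4 | Ratio | Variance saved | CI width saved |
|---|---|---|---|---|---|
| 0.4 | 0.54 | 0.39 | 0.722 | 28% | 15% |
| 0.5 | 0.50 | 0.375 | 0.750 | 25% | 13% |
| 0.6 | 0.44 | 0.34 | 0.773 | 23% | 12% |
| 0.8 | 0.26 | 0.21 | 0.808 | 19% | 10% |

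The CI column is 1 − √ratio. At ρ = 0.5 with 18 per arm, the standard error falls from √(2 × 0.50/18) = 0.236 SD to √(2 × 0.375/18) = 0.204 SD.

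**3. If Visits 5 and 6 behave differently.** For an equal-weight average, the bracket becomes the variance of the four-visit mean minus its squared covariance with baseline (baseline variance 1).

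- SD at Visits 5 and 6 higher by 20%, ρ = 0.6: 0.848 − 0.66² = 0.412 against 0.44, a saving of 6%.
- Same SD, ρ = 0.8: 0.255 against 0.26, a saving of 2%.
- Same SD, correlation 0.8 within each visit type and 0.7 between types: 0.969 − 0.82² = 0.297 against 0.26, an increase of 14%.
- Equal SD, correlation (or its serial part) halving every four weeks: about 9-11% saved for the equal-weight average, and about 0.5-4% for a common effect.

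**4. The acute and chronic coefficients.** With complete data the gain at Visit 4 or Visit 8 alone is 0%. With week-12 values missing, the chronic variance in σ² units at 18 per arm falls from 0.0926 to 0.0907 (2%; ρ = 0.5, 10% missing) and from 0.0500 to 0.0469 (6%; ρ = 0.8, 20% missing), comparing Visits 3 and 8 with Visits 3, 4, 5, 6 and 8. Part of that comes from Visit 4: with Visits 3, 4 and 8 the figures are 0.0916 and 0.0480.

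**The case against.** The models match the stated objectives. The SAP defines acute as baseline to Visit 4 and chronic as baseline to Visit 8, and those two estimates do not need Visits 5 and 6. This stands, and it is why 1.1 and 1.3 should not be replaced.

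There is also a documented reason to treat Visits 5 and 6 separately. Visits 3, 4 and 8 are fasting visits under a euglycemic clamp, with a modified diet scheduled beforehand, and the protocol justifies the sodium target by the risk of confounding neurohormonal measurements. A visit factor removes a common shift in mean. It does not remove a treatment-by-condition interaction or a difference in variance. This stands too: an average over all four visits mixes conditions. It does not undo the visit-specific comparisons, because both arms attend the same visits under the same conditions and each arm difference remains a randomized one.

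Three stronger readings are tempting, and the documents do not support them.

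- *The Visit 5 and 6 data go unreported.* Protocol section 7.3 says that mandated laboratory results and vital signs will be summarised in the clinical study report. They are absent from the efficacy models only.
- *The trial gives up a quarter of its precision.* That is a variance figure near ρ = 0.5, under equal correlation, for one exploratory estimate.
- *The primary question of persistence is weakened.* That question concerns proximal natriuresis measured by FE(Li), and lithium is taken only before Visits 3, 4 and 8.

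On AST, ALT, bicarbonate and chloride, the protocol's general statement that routine biochemistry is drawn at each physiological assessment could be read to cover Visits 4 and 8. The gap is therefore possible, not established.

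**Conclusion.** The point holds as a limited one. For outcomes measured at all five visits, the exploratory overall effect uses two of four on-drug measurements without explanation. Using all four would save about 19-28% of its variance, or 10-15% of confidence-interval width, for ρ between 0.8 and 0.4. That range assumes equal variance and correlation across visits. If Visits 5 and 6 are noisier or less correlated with the others, a simple average may gain little or lose precision. The primary outcome is untouched. The acute and chronic coefficients change only if Visit 8 values are missing, and then by a few percent of variance.

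The schedule gap for AST, ALT, bicarbonate and chloride, and the conflict over HbA1c, do not depend on any assumed correlation. They must be settled before the analysis, because the planned models may otherwise have no post-baseline data for those outcomes.

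**What to change.** 1. Keep models 1.1 and 1.3 unchanged.
2. Pre-specify one supplementary mixed model, labelled exploratory, for SBP, DBP, heart rate, weight, waist, BNP, hemoglobin, hematocrit, creatinine and electrolytes. Use visit as a factor over Visit 3 and every on-drug visit where the outcome is measured (4, 5, 6, 8), with baseline constrained equal. Report the arm difference at each visit, and an on-drug average labelled as mixing clamp and non-clamp visits.
3. Analyse Strauss volume separately, as post-baseline percent change at each visit with no Visit 3 outcome, because it is already a change from baseline. Leave glucose out, since it is clamped at some visits and not at others.
4. Reconcile Appendix A with the section 2 Measurements list and SAP outcomes 3.3 and 3.8: state at which visits AST, ALT, bicarbonate, chloride and HbA1c are drawn and which model applies to each. Where on-drug values exist only at Visits 5 and 6, use the supplementary model.

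The cost is a few lines of SAP and no new data collection. The downsides are an average over unlike conditions and two more nominal contrasts per outcome, which the exploratory label should make plain.
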